# NOTE: Subjects may require additional visits one day post dose to assess PD effect for dose escalation.

- a Subjects may be rescreened if necessary. Rescreening is considered conducting screening tests outside of the 21-day screening window.
- b Clinical visits should be conducted within an approximately 2-day window (±2 days). All study procedures should occur before study drug administration except as indicated (i.e., PK/PD).

- c Follow-Up procedures are to occur approximately 4 weeks after last dose whether the subject completes the study or terminates early.
- d Subjects enrolled at sites in the United States (US) must sign HIPAA authorization prior to the conduct of any study-specific procedures.
- e Must be conducted within approximately 7 days of PTG-300 dosing. Screening serum iron parameters must be collected before phlebotomy. Note: the prephlebotomy serum ferritin level and TSAT will be used as the subject's individual phlebotomy threshold for the study, i.e., the designated level at which a phlebotomy will be considered.
- f If a subject meets pre-specified criteria for phlebotomy during a visit, schedule a phlebotomy as soon thereafter as possible.
- g Additional tests or examinations, including physical exams, may be conducted as necessary.
- h For women of childbearing potential only.
- i Iron Absorption A is conducted prior to starting PTG-300 (i.e., after the phlebotomy performed during the Screening period). Iron Absorption B should be conducted after approximately 4 to 6 weeks of PTG-300 treatment (one day after PTG-300 administration between Week 4 and Week 6). See Table 3 for the Iron Absorption substudy schedule of events.
- j Study drug administration: PTG-300 is administered weekly or twice weekly. See Section 7.1.2 for details for monitoring TSAT and dose escalation.
- k See Appendix 1 for list of clinical laboratory tests. At Visits 3, 5, and 7, tests will include chemistry and CBC panel only (no urinalysis).
-  These tests should be conducted every 4 weeks at each clinic visit as well as each time point that PTG-300 PK blood samples are collected. In addition, iron parameters must also be measured whenever a subject's dose is escalated (See Section 13.1 and Appendix 2). Additional tests may be obtained as outlined in *Individual Subject Dose and Schedule Escalation* in Section 7.1.2.
- m All sample collection for iron parameters, PK (PTG-300 concentrations) are conducted pre-dose at each clinic visit, with additional 1-day post-dose collections at Week 1 and following any dose escalation.

Table 3: Schedule of Assessments for Study PTG-300-06 — Iron Absorption Substudy (Parts A and B)

	Hours Post  Fe Dosing				
Assessment	0	4	8	12	24
 Fe administration a	X				
Iron parameters: Serum iron, serum ferritin, TSAT, transferrin and  Fe	X b	X	X	X	X
PTG-300 concentration c	X b	X	X	X	X
Vital signs	X			X	X
Adverse events	X			X	X

Note: Iron Absorption A is conducted prior to starting PTG-300 (i.e., after the phlebotomy performed during the Screening period). Iron Absorption B should be conducted after approximately 4 to 6 weeks of PTG-300 treatment (one day after PTG-300 administration between Week 4 and Week 6). Abbreviations: TSAT = transferrin saturation.

<sup>a During Iron Absorption B, Fe should be administered approximately one day after PTG-300 administration.

<sup>b Pre-Fe dosing.

<sup>c Only conducted during Iron Absorption B.

## 10. TREATMENT OF SUBJECTS

# 10.1. Description of Study Drug

This study is a single-arm, open-label study; there is no placebo or comparator used.

PTG-300 will be provided by Protagonist.

PTG-300 is formulated in an aqueous buffered solution and prefilled at 0.5 mL and 1.0 mL into a 1-mL glass syringe. Study drug will be administered by subcutaneous (SC) injections, using a needle and a pre-filled syringe.

Fe will be provided by Protagonist as a ferrous sulfate solution for oral administration.

## 10.2. Concomitant Medications

Subjects must receive appropriate care for HH including phlebotomy. Subjects should receive full supportive care for any other underlying conditions and all medications taken are recorded.

Investigational agents must have been discontinued at least 30 days prior to screening and are not allowed during the study. All concomitant medications received by the subject beginning 30 days prior to Screening should be collected.

## 10.2.1. Contraceptive Requirements

Women of childbearing potential (WOCBP) and men must use medically acceptable contraception (<1% annual failure rate) during the duration of the study and for 28 days after the last dose of study drug in the case of women and 90 days after the last dose of study drug in the case of men. Medically acceptable methods of contraception that may be used by the subject and/or partner include but are not limited to the following:

- Combined (estrogen and progesterone containing) hormonal contraceptives (for at least 3 months before screening) (oral, intravaginal, or transdermal)
- Progesterone-only hormonal contraception (oral, injectable, or implantable) associated with inhibition of ovulation
- Intrauterine device (IUD)
- Intrauterine hormone-releasing system (IUS)
- Surgically sterile (e.g., vasectomy, hysterectomy, bilateral salpingectomy, or bilateral oophorectomy at least 3 months before dosing)
- Sexual abstinence.

# 10.3. Treatment Compliance

Study drug accountability and reconciliation will be performed by the study staff and the study monitor(s).

## 10.4. Randomization and Blinding

This is a single-arm, open-label study; no randomization or blinding is used.

#### 11. STUDY DRUG MATERIALS AND MANAGEMENT

#### 11.1. PTG-300

Specific instructions about the storage, preparation, administration, and accountability of PTG-300 are provided in the Pharmacy Manual.

#### 11.1.1. Study Drug

PTG-300 is provided by Protagonist in prefilled syringes containing PTG-300 in buffered saline solution. PTG-300 is formulated as an aqueous buffered solution, sterilized by filtration, and dispensed into 1 mL glass syringes at a 0.5 mL or 1.0 mL fill volume to deliver doses of 10 mg, 20 mg, and 40 mg. For an 80-mg dose, two 40-mg injections will be administered. Each solution is buffered with sodium acetate and adjusted to pH 5.4 with dilute acetic acid. The tonicity of each solution is adjusted with sodium chloride.

## 11.1.2. Study Drug Packaging and Labeling

PTG-300 will be provided in labeled syringes with one syringe per box.

## 11.1.3. Study Drug Storage

PTG-300 Injection must be stored at 2°C to 8°C, protected from light, in a locked area with limited access.

Storage instructions are included on the label. The Pharmacy Manual and Program Guide provide more detailed instructions on drug management.

#### 11.1.4. Study Drug Administration

Injection sites are SC tissue in the abdomen (2 inches away from the navel), triceps, or thighs. Sites should be rotated between injections.

Doses that are administered at the study site on clinic visit days will be given by a trained health care practitioner.

All doses should be administered in the clinic until the subject or caregiver demonstrates the ability to successfully administer PTG-300. Additionally, study drug should be administered in the clinic whenever the subject is scheduled for a dose on a clinic visit day.

#### 11.1.5. Study Drug Accountability

Compliance will be assessment throughout the study.

A record will be maintained by the investigational sites that will account for all dispensing and return of any used and unused study drug.

Investigators will be fully responsible for the security, accessibility, and storage of the study drug while it is at investigational sites. Investigators are also responsible for the education of study staff in the correct administration of the study drug.

### 11.1.6. Study Drug Handling and Disposal

Upon receipt of the study drug at the investigational site, it must be stored at 2°C to 8°C in a secure location with limited access.

At the end of the study the study drug will be reconciled, and a copy of the record given to the study monitor. Upon completion of the study any surplus study drug will either be returned to the Sponsor or be destroyed at the site upon receipt of written approval from Protagonist. Evidence of destruction must be supplied to the study monitor.

Further information of the storage, handling and administration of study drug will be provided in the Pharmacy Manual.

## 11.2. Fe Ferrous Sulfate Solution

Fe (approximately 4 mg) is provided by Protagonist as an oral ferrous sulfate solution.

Further information of the storage, handling, and administration of Fe will be provided in the Pharmacy Manual.

## 12. ASSESSMENT OF EFFICACY

## 12.1. Clinical Endpoints

#### 12.1.1. Phlebotomy and Iron Parameters

Intermittent therapeutic phlebotomy is standard of care for patients with HH. During the study the timing of a subject's phlebotomy will be based on their established TSAT and serum ferritin pre-phlebotomy threshold.

During the screening phase, subjects will have a phlebotomy within approximately 7 days prior to PTG-300 dosing. Each individual subject's pre-phlebotomy serum ferritin level will be used as their individual phlebotomy threshold, i.e., the designated level at which a phlebotomy may be performed in the study.

Subjects' iron parameters will be monitored throughout the study. A subject will receive a therapeutic phlebotomy during the study if his/her TSAT and serum ferritin is above their prephlebotomy level at Screening.

#### 12.1.2. Iron Absorption (Iron Absorption Substudy)

Subjects consenting to participate in the iron absorption substudy will have their iron absorption measured at two time points, pre-treatment with PTG-300 (Iron Absorption A) and after approximately 4 to 6 weeks of treatment with PTG-300 (Iron Absorption B). The purpose of the iron absorption substudy is to quantify the absorption of iron, marked by the Fe isotope and the effect of PTG-300 on absorption of iron following oral dosing.

## **12.2.** Quality of Life Instruments

## 12.2.1. Medical Outcome Study Questionnaire Short Form Health Survey (SF-36)

The Medical Outcome Study Questionnaire Short Form Health Survey (SF-36; Appendix 3) is a 36-item short-form (SF-36) questionnaire constructed to survey health status in the Medical Outcomes Study (MOS) (Ware 1992). The SF-36 includes one multi-item scale that assesses eight health concepts: 1) limitations in physical activities because of health problems; 2) limitations in social activities because of physical or emotional problems; 3) limitations in usual role activities because of physical health problems; 4) bodily pain; 5) general mental health (psychological distress and well-being); 6) limitations in usual role activities because of emotional problems; 7) vitality (energy and fatigue); and 8) general health perceptions.

#### 12.2.2. Patient Global Impression of Change (PGI-C)

Patient Global Impression of Change (PGI-C; Appendix 4) is a self-report measure that reflects a patient's belief about the efficacy of treatment. The patient will compare his/her condition from the start of the study on a 7-point scale ranging from "Very much worse" (1) to "Very much improved" (7) at the time of the assessment.

## 12.3. Anti-Drug Antibodies (ADA)

As PTG-300 is a protein drug, subjects may mount an immune response to PTG-300 producing ADA. Development of ADA will be monitored throughout the study. Samples will be obtained pre-dose at the time points specified in Table 2.

Should any subject develop ADA, an assessment will be made whether these are neutralizing and the impact of ADA on PTG-300's safety and efficacy in that subject will be evaluated.

# 13. PHARMACOKINETIC, PHARMACODYNAMIC AND IRON ABSORPTION ASSESSMENTS

Trough concentrations of PTG-300 by dose will be assessed. In addition, any additional pharmacokinetic parameters that can be estimated will be reported.

## 13.1. Blood Sample Collection Schedule in Each Study Period

## 13.1.1. Sample Collection for All Subjects

Blood draws to assess concentration of PTG-300 will be collected during each clinic visit prior to a dose of PTG-300 being administered and one day after PTG-300 dose escalation.

Blood draws to assess iron parameters will be collected during each clinic visit pre-dose PTG-300, and one day after each PTG-300 dose escalation.

See Schedule of Assessments, Table 2.

## 13.1.2. Sample Collection for Iron Absorption Substudy

Blood samples (5 mL) for measurement of Fe, will be collected at the following time points: 0 (pre-dose Fe) and at 4, 8, 12, and 24 hours post-dose Fe (within 10% nominal time).

Blood samples (5 mL) for measurement of iron parameters will be collected pre-dose Fe and at 4, 8, 12, and 24 hours post-dose Fe (within10% nominal time).

Blood samples (5 mL) for measurement of concentrations of PTG-300 will be obtained at the following time points during Iron Absorption B: at pre-dose Fe, and at 4, 8, 12, and 24 hours post-dose Fe (within 10% nominal time).

See Schedule of Assessments for Iron Absorption substudy, Table 3.

## 13.2. Samples Per Subject

Approximately 11 blood samples for PK and iron parameters (approximately 5 mL each) will be collected if a subject completes the entire study. In addition, blood samples will be taken for assessment of hematology and clinical chemistry. A total of approximately 160 mL of blood will be drawn over the 31-week study period for subjects who complete the study. Subjects that require dose escalation to 80 mg may have up to approximately 200 mL of blood collected over the 31-week study period. An additional 70 mL blood will be collected from subjects who complete the iron absorption substudy.

## 13.3. Pharmacokinetic Blood Sample Collection and Processing

See the Laboratory Manual for blood sample labeling, processing, storage, and shipment instructions.

#### 14. ASSESSMENT OF SAFETY

## 14.1. Safety Parameters

Safety will be assessed by the following parameters:

- ECGs, clinical laboratory tests including CBC (Appendix 1), and physical examinations findings (including vital signs).
- Adverse events and concomitant medications will be evaluated throughout the course of the study.
- Adverse events of interest will be assessed and reported separately and include the following: hematological toxicity > Grade 3 (CTCAE criteria, Version 5.0).

Vital signs will include blood pressure (systolic and diastolic), heart rate, respiratory rate, and temperature.

Electrocardiograms will include ventricular rate, PR, QRS, QT, RR and QTcF.

The specific timing of safety assessments is presented in Table 2.

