# 5.5. Summary of Potential Risks and Benefits

Based on the experience of PTG-300 dosing in nonclinical studies and a Phase 1 trial in healthy volunteers, the activities of PTG-300 are related to the proposed mechanism of action, allowing clinical monitoring. Immunologic responses to PTG-300 have not been observed in nonclinical species, however administration of PTG-300 carries theoretical liabilities (immunologically

based responses) associated with the systemic administration of a peptide. In the Phase 1 study PTG-300 was well tolerated, with the majority of AEs other than injection site reactions (primarily transient erythema) considered to be unrelated to PTG-300. In two ongoing Phase 2 studies in β-thalassemia patients, PTG-300 has been well tolerated with no safety concerns, and no deaths have been reported by subjects as of a cutoff date of September 1, 2020.

The potential risk in this study is causing anemia in subjects, assuming no iron is available for erythropoiesis.

The nonclinical and clinical data to date suggests that PTG-300 has a good safety profile and that PTG-300 may be effective for decreasing phlebotomy requirements and decreasing symptoms of iron overload. Thus, the potential benefits appear to outweigh the potential risks of PTG-300 and clinical testing of PTG-300 for HH is appropriate.

A subset of approximately 6 subjects will participate in an iron absorption substudy with the stable isotope Fe. Subjects will receive an oral administration of approximately 4 mg Fe as a ferrous sulfate solution. Stable isotopes are non-radioactive atoms of the same chemical element, which differ only in their number of neutrons (Bodamer 2001). Such studies are common in nutrition science and are often conducted to examine the absorption of selected elements (e.g., iron) from various foods and the impact of various diseases. These tracers are considered safe and may be particularly important for the validation of new treatment modalities, such as novel drug treatments (Bodamer 2001).

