# 7.2.1. Safety Criteria for Dose Interval Increase or Dose Reduction

The presence of at least one of the following criteria will require a dose reduction:

- CTCAE Grade 3 hematological toxicity or worsening of ≥2 grades in hematological parameters not clearly resulting from the underlying disease and/or without a clear-cut alternative that does not respond adequately to medical therapy.
- CTCAE Grade 3 non-hematological toxicities not clearly resulting from the underlying disease and/or without a clear-cut alternative that does not respond adequately to medical therapy.
- Treatment-related decrease of Hgb from baseline >20% or Grade 2 anemia, whichever is lesser, confirmed by a repeat value and not due to phlebotomy. Prior to resumption of PTG-300 at a reduced dose a follow-up Hgb should be assessed to confirm that Hgb has stabilized or improved to Grade 1.
- Investigator determines that the subject has experienced a clinically significant decrease in Hgb due to PTG-300.

If a treatment-related increase in aspartate aminotransferase (AST) or alanine aminotransferase (ALT) >3 × upper limit of normal (ULN) is seen, dosing with PTG-300 should be held, with resumption at a reduced dose if the AST and/or ALT levels return to baseline within 14 days; if the levels do not return to baseline within 14 days, an MRI should be conducted to assess whether there is an increase in iron accumulation.

Dose reduction has two steps. Initially subjects continue to receive the same dose of PTG-300 but the dosing frequency is reduced from twice weekly to weekly, or from weekly to every 2 weeks. If the subject continues to meet criteria for dose reduction, the dose is then decreased one dose level.

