# 7.2.2. PTG-300 Discontinuation or Stopping

The following are stopping criteria for an individual subject and will result in **discontinuation** of the subject from further treatment with study drug:

- Any CTCAE Grade 4 hematological or non-hematological toxicity not clearly resulting from the underlying disease and/or without a clear-cut alternative.
- CTCAE Grade 3 hematological toxicity or worsening of ≥2 grades in hematological parameters not clearly resulting from the underlying disease and/or without a clear-cut alternative persists over 7 days after adequate PTG-300 dose decrease.
- CTCAE Grade 3 non-hematological toxicities not clearly resulting from the underlying disease and/or without a clear-cut alternative explanation that do not improve within 14 days with maximal medical therapy and adequate PTG-300 dose decrease.
- When the Investigator in consultation with the medical monitor (MM) considers that is in the subject's best interest to discontinue treatment with PTG-300 (i.e., persistent, worsening or recurrent AEs).
- If a subject requires a dose reduction below 10 mg administered every 2 weeks.

- ALT, AST >5 × ULN and rising.
- ALT, AST remains >5 × ULN with no change in total bilirubin for more than 2 weeks.
- A worsening of clinical symptoms with no other acceptable explanation.
- The product meets Hy's Law:
  - Any test showing an increase of serum ALT >3 × ULN or >2 × ULN total bilirubin should be repeated within 48 to 72 hours for ALT, AST, alkaline phosphatase (ALP), and total bilirubin. If the repeat value for ALT or total bilirubin is unchanged or indicates decreasing activity, monitoring should continue at weekly intervals until the results are acceptable or normalized.
- Evidence of clinically meaningful increased iron accumulation in liver from baseline.

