## 14.2.1.1. Severity of an Adverse Event

Severity of adverse events will be assessed and reported following CTCAE Version 5.0 criteria (National Cancer Institute 2010). Severity of adverse events that do not match CTCAE criteria will be assessed as follows:

• Mild (Grade 1): awareness of sign or symptom but easily tolerated

- Moderate (Grade 2): discomfort enough to cause interference with usual activity
- Severe (Grade 3): incapacitating with inability to work or do usual activity
- Life-threatening (Grade 4): could reasonably lead to death without medical intervention
- Fatal (Grade 5)

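### The separately reported adverse event of interest starts above Grade 3, so it leaves out the Grade 3 hematological events that can trigger dose reduction or discontinuation

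*Combined protocol and SAP*

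**What the plan says.** Section 14.1 sets up a targeted safety report: "Adverse events of interest will be assessed and reported separately and include the following". One item follows, "hematological toxicity > Grade 3 (CTCAE criteria, Version 5.0". No other event of interest is listed.

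Section 5.5 names the hazard to be watched: "The potential risk in this study is causing anemia in subjects".

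Section 7.2.1 gives the dose-reduction criteria under the lead-in "The presence of at least one of the following criteria will require a dose reduction". The first is "CTCAE Grade 3 hematological toxicity or worsening of ≥2 grades in hematological parameters not clearly resulting from the underlying disease", with further qualifiers on alternative causes and on inadequate response to medical therapy. Grade 2 anemia, or a treatment-related hemoglobin fall of more than 20%, is also on that list.

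Section 7.2.2 discontinues a subject whose Grade 3 hematological toxicity (or worsening of two or more grades) "persists over 7 days after adequate PTG-300 dose decrease". It also discontinues for Grade 4 toxicity. Both rules carry attribution qualifiers.

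Section 15.8 summarizes all adverse events by system organ class and preferred term, with severity, seriousness and relationship shown in the same way. Neither Section 7.6.2 nor Section 15.8 mentions adverse events of interest.

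**The concern.** The only targeted safety category in the protocol addresses the on-target risk, yet it begins one grade above a level at which the protocol may already intervene. A subject could have Grade 3 hematological toxicity, have the dose reduced, and even be discontinued because the toxicity persisted, without entering the separate report.

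In a study of about 28 subjects an empty table is quite likely whenever Grade 4 events are uncommon. A reader who goes first to the events of interest could take an empty table as evidence of no important hematological toxicity. The general tables would correct that impression, but they list anemia, neutropenia and thrombocytopenia under separate preferred terms and are not planned to give one count of subjects with any Grade 3 or higher hematological event.

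**Working it through.** **Step 1. What the definition covers.** The fallback severity scale in Section 14.2.1.1 runs from Grade 1 to Grade 5 (fatal) and includes "Life-threatening (Grade 4): could reasonably lead to death without medical intervention". A strict inequality above Grade 3 therefore leaves Grades 4 and 5.

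**Step 2. The definition beside the action rules, for hematological toxicity.**

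| Event | Sections 7.2.1 and 7.2.2 (with their qualifiers) | In the Section 14.1 category as written | In the category if set to Grade 3 or higher |
|---|---|---|---|
| Grade 2 anemia, or Hgb fall >20% with anemia below Grade 3 | Dose reduction | No | No |
| Worsening of two or more grades, still below Grade 3 | Dose reduction; discontinuation if persistent | No | No |
| Grade 3 | Dose reduction; discontinuation if persistent | No | Yes |
| Grade 4 | Discontinuation | Yes | Yes |

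The Grade 3 row is the point. The first two rows show that moving the cut-off by one grade does not make the category equal to the Section 7.2.1 criteria.

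**Step 3. Could the symbol be a reading error?** The sign ≥ is preserved in comparable text, for example in "CTCAE Grade 3 hematological toxicity or worsening of ≥2 grades in hematological parameters", and Section 7.2.1 uses > as a strict inequality for the 20% hemoglobin fall. The Section 14.1 definition appears only once, so there is no second copy to compare. A misread symbol cannot be ruled out, but it cannot be assumed either.

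**Step 4. Illustration of size.** The plan gives no figure to reproduce. The one input from the documents is n = 28 (Sections 7.3 and 15.1). The rates are assumptions. Let p3 be the probability that a subject's worst hematological grade is 3, and p4 the probability that it is 4 or 5, with subjects independent.

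- At least one subject in the table as written: 1 − (1 − p4)^28
- At least one subject with Grade 3 included: 1 − (1 − p3 − p4)^28
- The difference is the chance that the table is empty although at least one subject had a Grade 3 event.

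| Assumed p3 | Assumed p4 | As written | With Grade 3 | Difference |
|---|---|---|---|---|
| 1% | 0.5% | 1 − 0.995^28 = 13.1% | 1 − 0.985^28 = 34.5% | 21.4 points |
| 5% | 1% | 1 − 0.99^28 = 24.5% | 1 − 0.94^28 = 82.3% | 57.8 points |
| 10% | 2% | 1 − 0.98^28 = 43.2% | 1 − 0.88^28 = 97.2% | 54.0 points |

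In all three scenarios the table as written is more likely than not to be empty, since each figure in the third column is below 50%.

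**The case against.** The strongest reply is that a reporting category and a management rule serve different purposes, and nothing in the documents says that their thresholds must agree. That is right, so this is a mismatch to reconcile and not a formal contradiction. It does not supply a reason for leaving Grade 3 out, and the documents give none.

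Second, Grade 3 events are reported elsewhere: by severity in Section 15.8, through the laboratory summaries, through the table of events leading to study discontinuation (Section 7.6.2), and through the dose-reduced action recorded for each event (Section 14.2.1.3). This stands. A reader might infer that Grade 3 toxicity would be hidden or lost; the documents do not support that. One caveat is that, under Section 14.2.4, an abnormal laboratory value that is neither judged clinically significant nor associated with signs or symptoms need not be recorded as an adverse event.

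Third, a reader might infer that the table as written could hold only events that ended treatment. That goes too far. The Grade 4 stopping rule depends on attribution and the Section 14.1 definition does not, so a Grade 4 event with a clear alternative cause would enter the table without forcing discontinuation. So would a Grade 4 event first arising in the four-week follow-up, after the last dose. In the same way, not every Grade 3 event requires dose reduction.

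Fourth, the list is introduced with wording that could be read as non-exhaustive, and Section 15 promises a SAP that takes precedence. No other item is listed, and no separate SAP text is in the material, so neither can be relied on to restore Grade 3.

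Finally, the rates in the illustration have no source in the documents. Section 5.2.2 lists no hematological event among those reported in more than 5% of the 63 β-thalassemia patients, which speaks against leaning on the highest scenario, although that is a different population.

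**Conclusion.** The point holds in a limited form. As written, the single listed adverse event of interest covers Grades 4 and 5 and omits Grade 3 hematological events, which can lead to dose reduction and, if persistent, discontinuation. The result is an incomplete targeted summary of the risk named in Section 5.5. It is not a loss of data.

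The size cannot be fixed from the documents. Over the assumed range, including Grade 3 raises the chance that the table shows at least one subject by about 21 to 58 percentage points. These figures rest on 28 treated subjects, independence and assumed rates. They describe whether one table is empty and do not measure bias in a safety conclusion. The top scenario should not be read as the expected case.

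It would also be wrong to infer that a cut-off at Grade 3 or higher brings the category fully into line with Section 7.2.1. For anemia in particular, that section can act at Grade 2.

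**What to change.** In Section 14.1, change the reporting category from > Grade 3 to ≥ Grade 3, after the sponsor confirms which symbol was intended, and carry the same definition into the SAP as a named table giving the number of subjects with any such event. State that the category does not capture the lower-grade criteria in Section 7.2.1 (Grade 2 anemia, a hemoglobin fall of more than 20%, or worsening of two or more grades that stays below Grade 3), so that the table is not presented as a count of all protocol-defined triggers.

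The cost is one symbol in the protocol and one table filter. No additional data need be collected, and the dosing and stopping rules stay as they are.
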